4.1.3. Per-protocol Set for analysis of immunogenicity

The per-protocol set (PPS) cohort for analysis of immunogenicity will be defined by timepoint (Day 31, Day 61 and End of the first RSV transmission season) and will consist of all subjects from the ES who complied with eligibility criteria, study procedures up to the end of the study and had immunogenicity results in the epoch as described below,

More specifically, the PPS cohort for analysis of immunogenicity for specific timepoint (Day 31 [Visit 3], Day 61 [Visit 5] and at end of the first RSV transmission season [Visit 7]) will include all evaluable subjects:

- Who met all eligibility criteria (i.e., no protocol violation linked to the inclusion/exclusion criteria, including age).
- Who received study vaccine as scheduled per protocol.
- For whom the administration route and site of the vaccine was as according to protocol.
- Who received the vaccine according to protocol procedures.
- Who complied with the vaccination schedule, as specified Table 4 in of the SAP.
- Who did not receive a concomitant medication/product/vaccine leading to exclusion from a PPS analysis, as described in Section 7.6.2 of the protocol, up to Day 31 (Visit 3)/up to Day 61 (Visit 5) /at Visit 7 (end of the first RSV transmission season).
- Who complied with the timings of the post vaccination blood sampling for immune response evaluation, up to Day 31 (Visit 3)/up to Day 61 (Visit 5) /at Visit 7 (end of the first RSV transmission season), as specified in Table 4 of the SAP.

When presenting different time-points, the PPS for immunogenicity will be adapted for each time-point (Day 31, Day 61 and End of first RSV transmission season).

Table 4 presents the intervals between study visits that determine subjects' eligibility for inclusion in the PPS analysis.

Table 4 Maximum allowed interval between study visits for PPS

Interval	Allowed length of interval ¹
Visit 1 (Day 1) → Visit 3 (Day 31)	23 - 44 days
Visit 1 (Day 1) → Visit 5 (Day 61)	60 - 81 days
Visit 3 (Day 31) → Visit 5 (Day 61)	28 - 37 days ²
Visit 5 (Day 61) → Visit 7 (end of the first RSV transmission season)	90 days to the defined end of transmission season or up to 4 weeks after

¹ Subjects will not be eligible for inclusion in the PP cohort for analysis of immunogenicity if they make the study visit outside this interval.

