4.2.3. Elimination from Per-protocol analysis Set (PPS)

4.2.3.1. Excluded subjects

A subject will be excluded from the PPS analysis under the following conditions

For codes 1040, 1070, 1080, 1090, 2040, 2060, 2070, 2080: subjects will be eliminated from a specific visit (at which the condition is met) onwards.

For codes 2090, 2100, 2120: subjects will be eliminated at the specific visit at which the condition is met

Code	Condition under which the code is used	Visit (timepoints) where the code is applicable	Applicable for analysis set
800	Fraudulent data	All	All
900	Invalid informed consent	All	all
1030	Study vaccine not administered at all	All	Safety, immunology
1040	Administration of concomitant vaccine(s) forbidden in the protocol:- 
 • Any investigational or non-registered product (drug or vaccine) other than the study vaccines used during the study period • A vaccine not foreseen by the study protocol administered during the period starting 30 days before the first dose and ending 30 days after the last dose of vaccine*, with the exception of: 
 – Scheduled routine pediatric vaccines which may be administered \geq 7 days before a dose and \geq 7 days after a dose of study vaccines, with the exception of live viral vaccines which may be administered 	Visit 3,5, 7	Immunogenicity

Code	Condition under which the code is used	Visit (timepoints) where the code is applicable	Applicable for analysis set
	≥ 14 days before a dose or ≥ 7 days after a dose. – Vaccines needed for urgent individual medical need (e.g., rabies prophylaxis)		
1050	Randomisation failure	All	Immunogenicity
1060	Randomisation code was broken	All	Immunogenicity
1070	Subjects got vaccinated with the correct vaccine but containing a lower volume	All	Immunogenicity
1070	Vaccination not according to protocol: 
Wrong replacement or study vaccine administered (not compatible with the vaccine regimen associated to the treatment number)Site or route of study vaccine administration wrong or unknownAdministration not according to protocol for reason specified by the investigator, other than side, site and route	All	Immunogenicity
1080	Vaccine temperature deviation (vaccine administered despite a Good Manufacturing Practices (GMP) no-go temperature deviation for RSV vaccines only)	All	Immunogenicity
1090	Expired vaccine administered (only applicable for RSV vaccine)	All	Immunogenicity

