2010	Protocol violation (inclusion/exclusion criteria including age)	All	Immunogenicity
2040	Administration of any medication forbidden by the protocol: 
Any investigational or non-registered product (drug) other than the study vaccines used during the study periodLong-acting immune-modifying drugs administered at any time during the study periodImmunosuppressants or other immune-modifying drugs administered chronically (i.e., more than 14 days in total) during the study periodImmunoglobulins and/or any blood products administered during the study period	Visit 3, 5, 7	Immunogenicity
2050	Underlying medical condition forbidden by the protocol	Visit 3, 5, 7	Immunogenicity
2060	Intercurrent medical condition → Intercurrent medical condition that has the capability of altering immune response, or alteration of initial immune status (suspected or confirmed immunosuppressive or immunodeficient condition) which may influence immune response	Visit 3, 5, 7	Immunogenicity
2070	Concomitant infection not related to the vaccine which may influence immune response	Visit 3, 5, 7	Immunogenicity
2080	Subjects did not comply with vaccination schedule:- Number of days between dose 1 and dose 2 is outside [23-44 days]	Visit 3	Immunogenicity

Code	Condition under which the code is used	Visit (timepoints) where the code is applicable	Applicable for analysis set
2090	Subjects did not comply with blood sample schedule 
 Number of days between dose 1 and visit 3 blood sample is outside [23-44 days] Number of days between dose 1 and visit 5 blood sample is outside [60-81 days] Number of days between dose 2 and visit 5 blood sample is outside [28-37 days] for RSV 2D group Number of days between visit 5 blood sample and visit 7 blood sample is outside [92-148 days] 	Visit 3, 5, 7	Immunogenicity
2100	Serological results not available post-vaccination:- No immunological result at visit x for all 2 tests - RSV A Neutralising antibody titer and RSVPreF3-specific IgG antibody concentration	Visit 3, 5 and 7	Immunogenicity

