5.2. Immunogenicity

5.2.1. Analysis of immunogenicity planned in the protocol

The primary analysis will be performed on the PPS for immunogenicity and, if in any group the percentage of vaccinated subjects with serological results excluded from the PPS for immunogenicity is more than 10%, a second analysis will be performed on the ES. The results from immunogenicity analysis will be reported by the pooled RSV vaccine group and the pooled comparator group

For the final analysis, the Adapted PPS for immunogenicity analysis will be used which allows the summary of immunogenicity results by time point. In summary table on the Adapted PPS for immunogenicity, immunogenicity summary result at Day 31, Day 61 and end of first RSV transmission season will be presented on PPS for immunogenicity at Day 31, Day 61 and end of first RSV transmission season, respectively.

The infants are monitored for RSV infection starting from dose 1 and, therefore, immunogenicity analyses can be adjusted to exclude those infants with an infection prior to sampling.

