8. CHANGES FROM PLANNED ANALYSES

Following are few changes from planned analysis:-

- In the protocol, we have PPS up to Day 61 which included Day 31 as well. To have better clarity with respect to PPS for Day 31, the text has been re-worded for the definition of PPS population. PPS has also been defined for Day 31 timepoint along with PPS at Day 61 and end of 1st RSV transmission season. Also, as the timepoint 'End of 1st RSV transmission season is not exactly Day 365, so the Day 365 has been removed and only kept as PPS at end of 1st RSV transmission season. The criteria of eliminating subject from the PPS of respective timepoint is accordingly reworded.
- In the protocol amendment 3, it is mentioned under Analysis of Immunogenicity section that 'In summary table on the Adapted PPS for immunogenicity, PPS for immunogenicity at Day 61 will be used for Pre, Day 31 and Day 61 immunogenicity summary and PPS for immunogenicity at Day 365 for Day 365 immunogenicity summary.' As we have added the PPS for Day 31 in the SAP, accordingly the summary table presentation has been modified as 'In summary table on the Adapted PPS for immunogenicity, immunogenicity summary result at Day 31, Day 61 and end of first RSV transmission season) will be based on PPS of Day 31, Day 61 and end of first RSV transmission season, respectively'.
- Table to present percentage of responders in terms of neutralizing antibody titers with 95% CI has been removed as there is no definition of response available.

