10.1.3.2. Age at vaccination in months

When age at vaccination is to be displayed in months, it will be calculated as the number of complete calendar months between the date of birth (DOB) and the date of vaccination. For example:

DOB = 10JUN2017, Date of vaccination = 09JUL2018 -> Age = 12 months

DOB = 10JUN2017, Date of vaccination = 10JUL2018 -> Age = 13 months

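### Code 2090's fixed 92-148 day Visit 5 to Visit 7 window contradicts Table 4 and would exclude most on-schedule infants from the end-of-season per-protocol set

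*SAP*

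**What the plan says.** SAP section 4.1.3 defines the per-protocol set (PPS) for immunogenicity separately at Day 31, Day 61 and the end of the first RSV season. It requires post-vaccination sampling to meet the intervals in Table 4. For Visit 5 to Visit 7, Table 4 allows "90 days to the defined end of transmission season or up to 4 weeks after". Its first footnote makes this binding: "Subjects will not be eligible for inclusion in the PP cohort for analysis of immunogenicity if they make the study visit outside this interval".

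Section 4.2.3.1 lists the codes that identify excluded subjects. Under code 2090, one ground for exclusion is: "Number of days between visit 5 blood sample and visit 7 blood sample is outside [92-148 days". The scope is limited: "For codes 2090, 2100, 2120: subjects will be eliminated at the specific visit at which the condition is met".

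Section 5.2.1 makes the PPS the primary set for immunogenicity. If more than 10% of vaccinated subjects with serology are excluded in any group, "a second analysis will be performed on the ES".

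Two other places bear on the expected interval. Table 1 puts Visit 5 at 8-9 months of age and Visit 7 at 14-18 months. Section 8 says the last timepoint used to be called Day 365, which was not exact, "so the Day 365 has been removed and only kept as PPS at end of 1st RSV transmission season".

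**The concern.** Table 4 and code 2090 govern the same exclusion and give different windows: one moves with the country's season, the other is a fixed number of days. The other three intervals under code 2090 (23-44, 60-81 and 28-37 days) carry the same limits as Table 4. Only the Visit 7 interval departs. Section 8 sets out the changes to the PPS, including the end-of-season timepoint, and mentions no fixed window. This looks like an oversight, not a decision.

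The humoral response at the end of the first season is a secondary endpoint, and its primary analysis is on the Visit 7 PPS. If the fixed window lies below the interval that the schedule produces, that set loses most of its infants for being on schedule.

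**Working it through.** Inputs: code 2090 limits 92 and 148 days (section 4.2.3.1); Table 4 limits, 90 days and season end plus 28 days (section 4.1.3); ages 8-9 and 14-18 months (Table 1); Visit 1 to Visit 5 interval 60-81 days (Table 4); target of 50 infants per pooled group (Table 2). One month = 365.25/12 = 30.44 days.

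1. **Can 92-148 be reproduced?** It equals 120 ± 28 days, but the SAP states no 120-day target. Let S be the days from Visit 5 to season end, so that Table 4 allows 90 to S + 28.
   - S + 28 = 148 requires S = 120, that is Day 61 + 120 = Day 181. Table 4 then gives 90-148, and the rules differ only at the lower limit (90 against 92).
   - S = 180 gives 90-208; S = 240 gives 90-268. Code 2090 rejects everything above 148.
   - S = 90 gives 90-118. Code 2090 then accepts samples up to 30 days later than Table 4 does.

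2. **What code 2090 implies.** Visit 7 would fall at Day 61 + 92 = 153 to Day 61 + 148 = 209. From a Visit 5 age of 8-9 months, Visit 7 age would be 8 + 92/30.44 = 11.0 to 9 + 148/30.44 = 13.9 months. Table 1 plans 14-18.

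3. **Table 1 at face value.** Shortest interval: 14 − 9 = 5 months = 152 days. Longest: 18 − 8 = 10 months = 304 days. None falls within 92-148.

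4. **Table 1 as completed months.** Section 10.1.3.2 derives age at vaccination this way: "it will be calculated as the number of complete calendar months between the date of birth (DOB) and the date of vaccination". If Table 1 follows the same convention, Visit 5 is 8.0 to <10.0 months and Visit 7 is 14.0 to <19.0. The interval runs from 4 months = 122 days to 11 months = 335 days. Only 122-148 overlaps.

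5. **Share retained, completed months, ages assumed uniform and independent.** Let x = 10 − Visit 5 age (0 to 2) and y = Visit 7 age − 14 (0 to 5). The interval is 4 + x + y months. The limit is 148/30.44 = 4.862 months, so an infant is kept if x + y ≤ 0.862.
   - All ages: (0.862²/2)/(2 × 5) = 0.372/10 = 3.7%.
   - Every Visit 7 at 14.0-15.0 months: 0.372/2 = 18.6%.
   - Every Visit 7 at exactly 14.0 months: 0.862/2 = 43.1%.
   - Visit 7 at 15.0 months or later: the interval is at least 5 months = 152 days, so 0%.

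6. **Varying Visit 5 within Table 4.** Take enrolment uniform over 6.0 to <8.0 months and Visit 7 uniform over 14.0 to <19.0.
   - Visit 5 always at 60 days: 3.5%.
   - Visit 5 spread uniformly over 60-81 days: 7.1%.
   - Visit 5 always at 81 days: the oldest Visit 5 age is 8 + 81/30.44 = 10.66 months, so x + y ≤ 4.862 − 3.339 = 1.523 and (1.523²/2)/10 = 11.6%.

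7. **Former Day 365 label.** 365 − 61 = 304 days, which is 304 − 148 = 156 days above the upper limit.

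8. **In infants.** Of 50 per pooled group, 3.7% is 1.9 and 11.6% is 5.8, so about two to six per group before any other loss.

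**The case against.** The strongest objection concerns size. Visit 7 is set by the end of each country's season, and those dates are in the SPM, not in the SAP. Table 1's ages assume enrolment at 6 and 7 months and are approximate. The result that nobody qualifies rests on a gap of 152 − 148 = 4 days at one corner of the face-value reading. This stands: a reader might infer that the end-of-season set would be empty, and the documents do not support that. A country with Visit 7 close to 14.0 months could keep a sizeable minority.

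Three further inferences are tempting and also go too far.
- That the Exposed Set replaces the PPS. Section 5.2.1 makes it an additional analysis. End-of-season data would still be reported, but the per-protocol result would not be repaired.
- That code 2090 is the rule that will be programmed. The SAP gives no precedence: codes identify eliminated subjects, but the Table 4 footnote is equally explicit.
- That the retained infants would cluster by country or season length. This is plausible, but cannot be shown without the season dates.

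The consequence is also bounded. Code 2090 acts only at the visit concerned, the endpoint is secondary and its analysis descriptive, and the safety and RSV infection analyses use Exposed Set populations. The 90 against 92 day difference has little effect by itself. None of this removes the contradiction in the upper limit.

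**Conclusion.** The concern holds as an internal contradiction with a material effect at one timepoint. Table 4 and code 2090 cannot both be applied unless the season happens to end about 120 days after Visit 5. Both the planned ages and the former Day 365 label point to longer intervals.

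Applied as written, code 2090 would remove most on-schedule infants from the end-of-season PPS: all of them on face-value ages, and roughly 88% to 96.5% on completed-month ages. The second range assumes uniform, independent ages. Under that convention the retained share rises to about 19% where every Visit 7 falls at 14.0-15.0 months, and to about 43% if all fall at exactly 14.0. The true share cannot be fixed without the SPM season dates.

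**What to change.** In code 2090, replace the fixed 92-148 days with the season-anchored window of Table 4, which the PPS definition already names for sample timing. Derive the limits per country from the SPM season dates.

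Clarify Table 4 at the same time. State from which date the 90 days are counted, whether a sample taken at 90 days but well before season end counts as an end-of-season sample, and that the upper limit is season end plus 4 weeks. Without this, the aligned rule could still admit samples that do not represent the end of the season.

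If 92-148 days was intended, reconcile Tables 1 and 4 to it and state the reason.

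Make the change before the Visit 7 analysis, and preferably before the Day 61 analysis, when section 7.1 unblinds the statistician, so that nobody chooses the window knowing the assignments. The cost is a short SAP amendment, one programming rule and a table of country season dates. No new data are needed.

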5. STATISTICAL ANALYSES

Note that standard data derivation rules and stat methods are described in “business rules document” and will not be repeated below. The study specific data derivation rules and stat methods will be described in section 9.

5.1. Demography

5.1.1. Analysis of demographics/baseline characteristics planned in the protocol

The analysis of demographics will be performed on the ES and on the PPS cohort for immunogenicity for each RSV + comparator vaccine group and each active control comparator group and also for the pooled RSV vaccine and pooled comparator group.

Demographic characteristics (age at vaccination in months, sex, country and race and vital signs), cohort description will be summarized by group using descriptive statistics:

- Frequency tables will be generated for categorical variables such as race.
- Mean, median, standard deviation and range will be provided for continuous data such as age.

The distribution of subjects will be tabulated as a whole and per group.

Withdrawal status will be summarized by group using descriptive statistics:

- The number of subjects enrolled into the study as well as the number of subjects excluded from PP analyses will be tabulated.
- The numbers of withdrawn subjects will be tabulated according to the reason for withdrawal.

5.1.2. Additional considerations

- Summary of important protocol deviation leading to elimination will be presented. An individual listing will also be presented for this.
- Consort tables for flow of subject from enrolment to randomization and randomization to exposed will also be presented.
- The following table will be performed for web public disclosure
 - Percentage of Enrolled subjects by country will be tabulated by group,
 - Percentage of Enrolled subjects by age categories will be tabulated by group.

5.2. Immunogenicity

5.2.1. Analysis of immunogenicity planned in the protocol

The primary analysis will be performed on the PPS for immunogenicity and, if in any group the percentage of vaccinated subjects with serological results excluded from the PPS for immunogenicity is more than 10%, a second analysis will be performed on the ES. The results from immunogenicity analysis will be reported by the pooled RSV vaccine group and the pooled comparator group

For the final analysis, the Adapted PPS for immunogenicity analysis will be used which allows the summary of immunogenicity results by time point. In summary table on the Adapted PPS for immunogenicity, immunogenicity summary result at Day 31, Day 61 and end of first RSV transmission season will be presented on PPS for immunogenicity at Day 31, Day 61 and end of first RSV transmission season, respectively.

The infants are monitored for RSV infection starting from dose 1 and, therefore, immunogenicity analyses can be adjusted to exclude those infants with an infection prior to sampling.

5.2.1.1. Within groups assessment

5.2.1.1.1. Analysis of secondary objectives

For three pooled groups, at each timepoint that blood samples are collected for humoral immune response against the investigational RSV vaccine (neutralizing antibody titers against RSV-A, RSV F antibody concentrations).

- Geometric mean titers/concentrations (GMTs/GMCs) will be tabulated with 95% CI and represented graphically.
- Percentage of subjects above the sero-positivity threshold will be tabulated with exact 95% CI.
- Antibody titers/concentrations will be displayed using reverse cumulative curves.
- The distributions (< 128, 128-256, > 256-512, > 512-1024, > 1024-2048, > 2048-4096, > 4096) of neutralizing antibody titers/concentrations will be tabulated.
- Individual post-vaccination versus pre-vaccination results will be plotted using scatter plots. Results of the comparator group will be used as a reference.
- Geometric mean of ratios of antibody titers/concentrations at each post-vaccination timepoint over pre-vaccination will be tabulated with 95% CI.
- Distribution of the fold increase of the neutralizing antibody titers will be tabulated by pre-vaccination titer category.
- The kinetics of individual antibody titers/antibody concentrations results will be plotted as a function of time for subjects with results available at all timepoints.

An immunogenicity analysis will also be performed on the ES with a negative RSV exposure status (at screening based on in-stream baseline serological testing) for whom immunogenicity data are available.

At study end, an additional analysis of immunogenicity will be performed on infants by baseline values (as per the cut-off used to define RSV naïve serostatus).

5.2.1.1.2. Analysis of tertiary objective

If available, any further exploratory immunology results (including, but not limited to anti-vector immunity and palivizumab-competing antibody concentrations) will be reported by timepoint for the two pooled RSV vaccine groups and the pooled comparator group using descriptive summary statistics.

5.2.2. Additional considerations

- Summary statistics for neutralizing antibody titers against RSV-A, RSV F antibody concentrations (Minimum, Mean, median, SD, 1st quartile, 3rd quartile, Maximum) will be presented.
- Distribution of the fold increase of the neutralizing antibody titers will be tabulated by pre-vaccination titer category (percentage of subjects with a fold increase equal to

or above 1, 2, 2.5, 3, 4, 6, 8 10, 11 and 12 by pre-vaccination titre category: (< 128, 128-256, > 256-512, > 512-1024, > 1024-2048, > 2048-4096, > 4096, and by cumulative category: <128, ≥128, ≥256, ≥512, ≥1024, ≥2048, ≥4096.). The thresholds for presentation of titres in distribution table and for fold increase will be further adjusted at Day 61 analysis as needed.

- For three pooled groups, at each timepoint that blood samples are collected for humoral immune response against the investigational RSV vaccine (neutralizing antibody titers against RSV-A, RSV F antibody concentrations, following additional analysis will be performed on PPS by baseline values (sero-negative vs sero-positive for RSV as per cut-off defined for RSV naïve serostatus) at the end of study:-
 - Geometric mean titers/concentrations (GMTs/GMCs) will be tabulated with 95% CI and represented graphically.
 - The distributions of neutralizing antibody titers/concentrations will be tabulated.
 - Geometric mean of ratios of antibody titers/concentrations at each post-vaccination timepoint over pre-vaccination will be tabulated with 95% CI
 - Summary statistics for neutralizing antibody titers against RSV-A, RSV F antibody concentrations (Minimum, Mean, median, SD, 1st quartile, 3rd quartile, Maximum) will be presented.

